##### b) Cerebral Hemorrhage

Hemorrhages in the CNS are classified as stroke if they are nontraumatic, caused by a vascular event, and result in injury to the CNS. In contrast, traumatic hemorrhages will not be characterized as stroke. Subdural hematoma will not be classified as a stroke.

The diagnoses included in this section are intracerebral hemorrhage (intraparenchymal and intraventricular) and subarachnoid hemorrhage (both aneurysmal and nonaneurysmal).

Diagnoses included in this section are not part of the primary endpoint.

- Stroke caused by intracerebral hemorrhage

Rapidly developing clinical signs of neurological dysfunction (focal or global) attributable to a focal collection of blood within the brain parenchyma or ventricular system that is not caused by trauma.

- Stroke caused by subarachnoid hemorrhage

Rapidly developing signs of neurological dysfunction (focal or global) and/or headache because of bleeding into the subarachnoid space (the space between the arachnoid membrane and the pia mater of the brain or spinal cord), which is not caused by trauma.

Hemorrhages may be further classified according to location (example, supratentorial, subtentorial, intraparenchymal etc.)

- c) Stroke not otherwise specified

An episode of acute neurological dysfunction presumed to be caused by ischemia or hemorrhage, persisting  $\geq 24$  hours or until death, but without sufficient evidence to be classified as one of the above.

Strokes not otherwise specified are part of the primary endpoint.

A functional disability assessment will be performed for strokes after 3 to 6 months following the start date of the event (see [Appendix I](#)).

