#### 10.4.4 General guidelines for reporting adverse events

- AEs are to be recorded in corresponding screen(s) included in the eCRF.
- The reporting requirement of AEs depends on patient status (study completer or patient who had premature permanent discontinuation of IMP)
  - In patients who receive IMP until the end of the study (study completer), all AEs, regardless of seriousness or relationship to IMP/NIMP, spanning from the signature of the informed consent form until the CSED visit are to be recorded in the eCRF. Patients who experience a new or ongoing related or serious AE or a new or ongoing AESI (see [Section 10.4.2](#)) at the CSED visit should be followed beyond the CSED visit until resolution, stabilization, or death (whichever comes first) and related data will be collected (see [Section 10.1.5.4.1](#)).
  - In patients who have permanent premature IMP discontinuation:
    - All AEs, regardless of seriousness or relationship to IMP/NIMP, spanning from the signature of the informed consent form until 6 months following V70 (end of treatment visit) are to be recorded in the eCRF.
    - From 6 months following V70 until the CSED visit, related and/or serious AEs should be recorded in the eCRF.

***NOTE:** Reporting requirement for suspected efficacy endpoints is the same regardless of patient status (study completers or patients who had premature permanent discontinuation of IMP); suspected efficacy endpoints should be reported in all randomized patients until the end of the study (CSED).*

- Whenever possible, diagnosis or single syndrome should be reported instead of symptoms. The Investigator should specify the date of onset, intensity, action taken with respect to IMP, corrective treatment/therapy given, additional investigations performed, outcome, and his/her opinion as to whether there is a reasonable possibility that the AE was caused by the IMP.
- When treatment is prematurely discontinued, the patient will be maintained in the study and the patient's observations will continue until the common study end date visit (see [Section 10.3.4](#)).
- Laboratory, vital signs or ECG abnormalities are to be recorded as AEs only if:
  - Symptomatic and/or
  - Requiring either corrective treatment or consultation, and/or
  - Leading to IMP discontinuation or modification of dosing (with exception of LDL-C levels which may lead to IMP dosing modification, but in a blinded manner), and/or

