3.1.4 Safety endpoints

Following injections are considered as double-blind IMP injections:

• For patients randomized in the placebo group: any injection from double-blind kits;

• For patients randomized in the alirocumab group: any injection from double-blind kits excepted placebo injections given to maintain the blind in case of 2 consecutive LDL-C values <15 mg/dL.

Of note potential additional training injections after randomization using training injection kits will not be taken into account.

The period of safety observation starts from the time when the patient gives informed consent and is divided into three periods:

- PRE-TREATMENT period: defined from the signed informed consent up to the first dose of double-blind IMP injection;
- Treatment-emergent adverse event (TEAE) period: defined as the time from the first dose of double-blind IMP injection to the last dose of double-blind IMP injection +70 days (10 weeks), (as residual effect of treatment is expected until 10 weeks after the stop of double-blind IMP).

The TEAE period will include:

- The TREATMENT period defined as the time from the first dose of double-blind IMP up to the day of last dose of double-blind IMP injection +21 days, as serum concentration of alirocumab >10 μ g/mL is expected for approximately 21 days following administration of 150 mg, and because throughout the previous studies it was observed that when alirocumab concentrations declined below this concentration, decrease in effect on LDL-C is observed.
- The RESIDUAL TREATMENT defined as the time from the day of last dose of double-blind IMP injection +22 days up to the day of last dose of double-blind IMP injection +70 days (10 weeks).
- POST-TREATMENT period: defined as the time starting the day after the end of the TEAE period.

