3.4.6 Analyses of other safety parameters

Events initially suspected by investigators, and reported as such in endpoints forms, may finally not be confirmed by investigators and possibly classified into another category that is not a component of the primary efficacy endpoint. In addition, per protocol all suspected UAs have to be sent for adjudication regardless of whether the event fulfils the stricter protocol definition or not, therefore a high proportion of the reported UAs are expected to be finally not retained as an endpoint.

Since those events are not reported as adverse events either, they will be described separately as follows:

The number (%) of patients with events below during the TEAE period will be displayed by treatment group on the safety population:

- With final diagnosis as per investigator of stable coronary disease,
- With final diagnosis as per investigator of unstable angina regardless of whether the event fulfils the stricter protocol definition or not;
- With final diagnoses as per investigator of hemorrhagic stroke, transient ischemic attack (TIA), and subdural hematoma.

The number (%) of patients with hemorrhagic strokes or silent MI as per CEC during the TEAE period will also be summarized on the safety population

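### Non-fatal hemorrhagic stroke is summarized only as a crude percentage in a treatment window that can end earlier in the alirocumab arm, although the data to compare both arms to study end should exist

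*SAP*

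**What the plan says.** - **Endpoint status.** Protocol 9.1.6.3 says of intracerebral and subarachnoid hemorrhage: "Diagnoses included in this section are not part of the primary endpoint". The main and other secondary endpoints (SAP 3.1.3.2) name only ischemic stroke among non-fatal strokes.
- **Adverse event status.** Protocol 10.4.3 sends suspected cardiovascular endpoints to endpoint forms. They are not treated as adverse events unless the investigator judges them unexpected. SAP 3.4.6 says of events on those forms that are not finally retained as endpoints: "Since those events are not reported as adverse events either, they will be described separately as follows".
- **Planned summary.** Investigator-diagnosed hemorrhagic stroke is counted by group in the treatment-emergent (TEAE) period. For adjudicated events, SAP 3.4.6 plans a number and percentage of patients with "hemorrhagic strokes or silent MI as per CEC during the TEAE period", on the safety population.
- **Window.** SAP 3.1.4 runs the TEAE period from first double-blind injection to last double-blind injection plus 70 days. In the placebo arm every double-blind kit injection counts. In the alirocumab arm the rule is "any injection from double-blind kits excepted placebo injections given to maintain the blind in case of 2 consecutive LDL-C values <15 mg/dL". SAP 3.5.1 likewise dates the last dose of a switched patient by the last active injection.
- **Collection.** Protocol 10.4.4 says "suspected efficacy endpoints should be reported in all randomized patients until the end of the study (CSED"). Protocol 9.1 sends suspected events and all deaths to the Clinical Events Committee (CEC).
- **Comparable events.** Venous thromboembolic and limb events get an ITT time-to-event (Kaplan-Meier) analysis with primary-endpoint censoring (SAP 3.1.5.7, 3.4.7.7). Tier 1 safety events get rates per 100 patient-years with intervals, Cox hazard ratios and Kaplan-Meier curves (SAP 3.4.5.1).

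**The concern.** Two features combine. First, the end of the window depends on arm by rule. An alirocumab patient switched to blinded placebo stops contributing 70 days after the last active dose, while a placebo patient who keeps injecting contributes throughout. Second, a percentage of patients ignores how long each was observed, so it cannot correct for this. Shorter observation in one arm lowers that arm's percentage, and here the arm is the active one and the event is a harm.

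There is also a mismatch within stroke. Ischemic and unspecified strokes count to CSED in all randomized patients, while non-fatal hemorrhagic strokes count only in the treatment window. The two outputs cannot be added to give an all-stroke comparison over one period. The plan accounts for unequal exposure elsewhere: Protocol 11.4.3.1 for selected adverse events, and SAP 3.4.5 for the analysis by dose.

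**Working it through.** **Plan figures.** The documents give no figure for hemorrhagic stroke, so none can be reproduced. The design's event target does reproduce: 4 × (1.960 + 1.282)² / (ln 0.85)² gives 1592 events before group-sequential inflation, against 1613 stated. Nothing below depends on it.

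**Inputs from the documents.** Monthly enrolment table and 40-month accrual (SAP 1.3); 64-month duration (SAP 1.1); 70-day extension (SAP 3.1.4), so L = 70/30.4375 = 2.30 months.

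**Assumed inputs.** Permanent discontinuation at a constant rate d of 2-10% per year, equal in both arms. Share s of the alirocumab arm switched: 0-10%, at t = 4 or 12 months. Hemorrhagic stroke rate: 0.05-0.2 per 100 patient-years, constant and the same in switched patients. Deaths and losses to follow-up are ignored.

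**Step 1, follow-up.** The table adds to 2004 + 29 × 560 = 18,244, scaled here to 18,000. With T = 64 − (m − 0.5) for patients enrolled in month m, mean follow-up to CSED is 40.4 months.

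**Step 2, share of follow-up inside the window.** With λ = d/12 per month, expected TEAE time is L + (1 − exp(−λ(T − L)))/λ, averaged over enrolment.

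| d per year | Mean TEAE months | Share inside | Outside |
|---|---|---|---|
| 2% | 39.15 | 96.9% | 3.1% |
| 4% | 37.95 | 93.9% | 6.1% |
| 8% | 35.71 | 88.4% | 11.6% |
| 10% | 34.67 | 85.8% | 14.2% |

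**Step 3, tilt from the arm-specific cut.** A switched patient has expected TEAE time W_s = (1 − exp(−λt))/λ + L. For a rare event the ratio of crude percentages at a true hazard ratio of 1 is (1 − s) + s × W_s/W, where W is the mean from step 2. Example with d = 4%, t = 4, s = 10%: W_s = 3.97 + 2.30 = 6.27, so the ratio is 0.90 + 0.10 × 6.27/37.95 = 0.917.

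| s | Ratio, d = 4-8%, t = 4-12 months |
|---|---|
| 0% | 1.00 |
| 2% | 0.983-0.988 |
| 5% | 0.958-0.969 |
| 10% | 0.917-0.939 |

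**Step 4, event numbers.** Person-time is 18,000 × 40.4/12, about 60,600 patient-years in both arms together. The last column is the 95% interval factor on the hazard ratio, exp(1.96 × 2/√events).

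| Rate per 100 patient-years | Events to CSED | Outside window (d = 4-8%) | Interval factor: CSED; TEAE |
|---|---|---|---|
| 0.05 | 30 | 2-4 | 2.04; 2.08-2.13 |
| 0.1 | 61 | 4-7 | 1.65; 1.68-1.71 |
| 0.2 | 121 | 7-14 | 1.43; 1.44-1.46 |

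The longer window gains little precision. Its value is a common observation period for both arms, with a rate and an interval attached.

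**The case against.** **The window is deliberate.** Residual effect is expected for 10 weeks after the last dose, and injections after the switch contain no drug, so closing alirocumab exposure there is coherent. An analysis to CSED adds off-drug time and may dilute a drug effect. This stands. It is a reason to show both views, and neither should be called unbiased without qualification. It does not answer the missing person-time denominator.

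**Fatal cases are covered.** Protocol 9.1.7.1 classes death from intracerebral hemorrhage as cardiovascular death. It therefore enters any CV event, CV death and all-cause death to CSED, and SAP 3.4.5.2 tabulates CEC causes of death to CSED. This also stands, and limits the point to non-fatal events. Neither output is stated to show hemorrhagic deaths separately.

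**The effect is small and the table is descriptive.** Correct. A tilt of at most about 8% is well inside the random error in step 4. Protocol section 4 expects few patients below 25 mg/dL, and the switch needs two values below 15 mg/dL, which points to the lower end of the assumed range.

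**Adjudication to CSED is inferred.** Also correct. It follows from the general collection and CEC rules, and from the need to classify each stroke before deciding whether it enters the primary endpoint. Protocol Appendix E and SAP Appendix C were not in the text available.

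**A stronger reading.** A reader might infer that the plan hides a recognised harm of very low LDL-C. The documents do not support this. Hemorrhagic stroke is not an adverse event of special interest, and it is not among the events SAP 3.4.5.1 pre-specifies for the low-LDL-C analysis. A known history of it is an exclusion criterion, but no link to LDL-C is stated.

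**Conclusion.** The point holds for non-fatal hemorrhagic stroke. Its planned summaries are crude percentages in a window that closes earlier, by rule, for switched alirocumab patients, and no rate, interval or analysis to CSED is specified.

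With equal discontinuation and equal underlying risk, the crude comparison leans toward alirocumab: a null ratio of about 0.98-0.99 if 2% are switched and 0.92-0.94 if 10% are. About 3-14% of follow-up lies outside the window at 2-10% per year discontinuation. All of this rests on assumed switch, discontinuation and event rates. If discontinuation differed between arms, the net lean could change.

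This is a modest reporting weakness. It does not touch the primary analysis, and it does not show that a harm would be missed.

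**What to change.** Add to the SAP a descriptive time-to-first-event analysis in the ITT population, from randomization to CSED, for:

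- CEC-adjudicated hemorrhagic stroke, fatal and non-fatal;
- all CEC-adjudicated stroke.

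Report events, rate per 100 patient-years, Kaplan-Meier curves, and a region-stratified Cox hazard ratio with 95% interval, using primary-endpoint censoring. This extends to hemorrhagic stroke the ITT time-to-event approach already planned for venous thromboembolic and limb events. Keep the SAP 3.4.6 table as the on-treatment view and add a rate per 100 patient-years to it. State that the two views answer different questions: the first includes off-drug time, the second follows active exposure.

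The cost is one further time-to-event run, a rate column and possibly one derived variable. If the collection and adjudication rules apply as inferred, no new data are needed. No alpha is spent.

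Before finalising, confirm against Protocol Appendix E and SAP Appendix C that hemorrhagic strokes are reported and adjudicated to CSED in all randomized patients.

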3.4.7 Analyses of other endpoints

All measurements, scheduled or unscheduled, fasting or not fasting, will be assigned to analysis windows defined in Section 3.5.4, in order to provide an assessment for Month 1 to Month 64 time points.

3.4.7.1 Analyses of hs-CRP

hs-CRP parameter will be summarized on the safety population by analysis visit using number of available data, mean, SD, median, Q1, Q3, minimum, and maximum for each treatment group during the treatment period. The time profile will be plotted by treatment group with the medians, Q1 and Q3. The incidence of PCSA at any time during the TEAE period will be summarized by treatment group using descriptive statistics.

hs-CRP values greater or equal to 10 mg/L will be excluded from analyses in a second approach, since these are suggestive of concurrent infections.

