
ASSESSMENT SCHEDULE
	
Visits scheduled during the run-in period:                  Please refer to Run-In Period section under 'Study Design'
 
Visits schedule during the double-blind treatment period:
 
 
• Clinic/On-site visits:                     
 
- For the first year: visit at Month1, Month 2, Month 4 and then every 4 months (Month 8, Month 12)
 
- For the second year: visit every 4 months
 
- For the subsequent years: visit every 6 months up to the end of the study
 
 
 
 
Contacts schedule during the double-blind treatment period:
 
 
• A phone call or contact via internet (as permitted by institutional privacy policies) should occur in between clinic visits throughout the study with the goal of maintaining a contact with the patient about every 2 months during first 24 months, and about every 3 months thereafter.
 

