### **9.3.3 hs-CRP**

The percent change in hs-CRP from baseline up to the common study end date.

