#### **10.1.5.4 Common study end date visit (Final Visit) – Visit 30 (~Month 64, between CSED and CSED + 30 days)**

This final CSED visit should be scheduled and be performed on or shortly after the actual occurrence of the CSED (see also [Section 6.2.2](#)). CSED is scheduled to occur at around Month 64, and will be announced by the sponsor in advance in order for sites to be able to plan this final visit.

This final CSED visit (Visit 30, Month 64):

- should be a clinic visit,
- should be performed for all randomized patients regardless of the patient status (still receiving IMP or having prematurely discontinued IMP permanently),
- however there are some differences on how to plan the visit (and last IMP injection, when applicable) and in assessments to be performed at that final visit, depending on patient status.

For patients still receiving IMP (study completers), both CSED visit and last IMP injection should be determined taking into account the following:

- CSED visit should take place between CSED and CSED + 30 days
- CSED visit should occur 14 days ( $\pm 3$  days) after last IMP injection
- Site has clearly communicated and agreed in advance with patient (and family) on date of last IMP injection and date of CSED visit

- In order to ensure compliance with these critical final study procedures, sites should:
  - contact patients a few days prior to the agreed-upon date of last IMP injection,
  - remind patient about the final IMP injection and final CSED visit, and
  - ask patient to return to the investigational site in the morning preferably in fasting condition (ie, overnight, at least 8 hours fast) and to bring the used and unused kits and the diary.

Assessments to be performed at the CSED visit for study completers are described in [Section 10.1.5.4.1](#).

For patients who had previously permanently discontinued IMP:

- CSED visit should take place between CSED and CSED + 30 days.
- Site has communicated and agreed in advance with patient (and family) on date of CSED visit.
- In order to ensure compliance with these critical final study procedures, sites should:
  - contact patients a few days prior to the final CSED visit, and
  - ask patient to return to the investigational site in the morning preferably in fasting condition (ie, overnight, at least 8 hours fast).

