The value at the CSED will be the value obtained at the CSED visit. For patients without CSED visit, the last lipid value observed or imputed up to CSED will be taken into account.

Throughout the ANCOVA and robust regression models, the alirocumab group will be compared to placebo using appropriate contrasts tested at the two-sided 0.05 level, and providing the 95% CI of the difference, for the different time points as well as at the CSED.

No adjustment will be made for lipid variables for which p-values will be provided for descriptive purpose.

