3.4.7.4.2 On-treatment analyses

Analysis of lipid variables will be conducted during the treatment period. Post-treatment data will not be considered.

The lipid variables other than Lp (a) and TGs will be analyzed in the randomized and treated population using a mixed-effect model with repeated measures (MMRM) approach. All post-baseline on-treatment data available within Month 1 to Month 64 analysis windows will be used and missing data will be accounted for by the MMRM model.

The model will include the fixed categorical effects of treatment group (placebo, alirocumab), planned time point (Month 1 to Month 64), treatment-by-time point interaction, as well as, the continuous fixed covariate of baseline lipid value and baseline lipid value-by-time point interaction. This model will be run using SAS Mixed procedure with an unstructured correlation matrix to model the within-patient errors. Parameters will be estimated using restricted maximum likelihood method with the Newton-Raphson algorithm. Denominator degrees of freedom will be estimated using Satterthwaite's approximation. This model will provide baseline adjusted least-squares means estimates over time for both treatment groups with their corresponding SEs and 95% CI. To compare the alirocumab group to the placebo group, appropriate contrasts statement will be used to test the differences of these estimates, at the 2-sided 0.05 level, for the different time points.

Note: in case of computation issue for this approach, multiple imputation under missing-at-random (MAR) assumption will be conducted, followed by an ANCOVA model.

The Lp (a) and TGs will be analyzed in the randomized and treated population using multiple imputation (same imputations as in Section 3.4.7.4.1 without discarding imputations of missing values during the post-treatment period (see Appendix F).

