3.5.4 Windows for time points

Data analyzed by time point (including lipid data, laboratory safety data, vital signs, ECG, ADA, EQ-5D) will be summarized using the time windows given in Table 8 below. These time windows will be applicable for all analyses, and they are defined to provide more homogeneous data for time point-specific analyses.

Statistical Analysis Plan SAR236553/REGN727-EFC11570 - alirocumab 11-Oct-2017 Version number: 3

Time point	Targeted study days	Time windows
Month 1	30	16 to 44
Month 2	60	45 to 75
Month 4	122	107 to 137
Month 8	244	229 to 259
Month 12 to Month 24	Number of months of the planned visit x 30.4375 and rounded to the nearest entire number of days	Targeted study day ±21 days
Beyond Month 24	Number of months of the planned visit x 30.4375 and rounded to the nearest entire number of days	Targeted study day ±28 days

Table 8 - Time windows definitions

If multiple valid values of a variable exist within a time window, the nearest from the targeted study day will be selected for the statistical analysis by time point. If the difference is a tie, the value after the targeted study day will be used. If multiple valid values of a variable exist within a same day, then the first value of the day will be selected.

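### The last on-treatment sample is drawn at a calendar date but analysed in fixed-month windows, so about 70% of these samples reach no time point for hs-CRP, HbA1c or on-treatment lipids

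*SAP*

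**What the plan says.** **Analysis rule.** The opening of SAP 3.4.7 allocates every measurement of the other endpoints to the Table 8 windows, for Months 1 to 64. For hs-CRP, SAP 3.4.7.1 states: "hs-CRP parameter will be summarized on the safety population by analysis visit using number of available data". SAP 3.4.7.2 treats HbA1c in the same way. For on-treatment lipids other than Lp(a) and triglycerides, SAP 3.4.7.4.2 fits a repeated-measures model: "All post-baseline on-treatment data available within Month 1 to Month 64 analysis windows will be used".

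**Windows.** Table 8 (SAP 3.5.4) centres each window on the planned month × 30.4375 days. The width is "Targeted study day ±21 days" for Months 12 to 24 and "Targeted study day ±28 days" after that.

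**Visits.** After the second year the protocol summary gives: "For the subsequent years: visit every 6 months up to the end of the study". The flow chart labels the final visit, V30, as Month 64. Protocol 10.1.5.4, however, ties it to the calendar: "CSED visit should take place between CSED and CSED + 30 days". For completers it falls 14 ± 3 days after the last injection.

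**Samples.** In the flow chart, hs-CRP and ApoA-1 are drawn at Months 0, 4 and 12, at V30 (completers) and at V70, the early end-of-treatment visit. ApoB is also drawn at Month 24. HbA1c is yearly, and the basic lipid panel is drawn at every clinic visit.

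**End of study.** Protocol 9.3.3 defines the hs-CRP variable as: "The percent change in hs-CRP from baseline up to the common study end date". Only the ITT lipid analysis (SAP 3.4.7.4.1) takes the final visit directly, whatever its timing: "The value at the CSED will be the value obtained at the CSED visit". SAP 3.4.5.3 gives a last on-treatment row, but for the safety laboratory variables, which do not include hs-CRP, HbA1c or lipids.

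**The concern.** V30 happens on nearly one date for everyone, so its study day depends on when the patient entered. The windows are fixed in study days and leave gaps between them. A V30 sample that falls in a gap belongs to no time point and drops out of the by-visit summaries and the repeated-measures model.

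These are valid on-treatment samples: V30 comes at most 14 + 3 = 17 days after the last injection, and the treatment period in SAP 3.1.4 runs to 21 days.

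For LDL-C and HbA1c one late point is lost from a long series. For hs-CRP and ApoA-1 the lost sample is the only scheduled on-treatment one after Month 12, and for ApoB the only one after Month 24. Their late time points would hold whichever patients entered at a date that put V30 inside a window. For ApoA-1 the unstructured covariance between late months would also have almost no data, since a patient normally contributes one on-treatment value after Month 12.

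**Working it through.** **1. Reproduce the plan's enrolment figure.** From protocol Table 3: 96 (Months 1–3) + 64 + 80 + 104 + 160 + 240 + 320 + 420 + 520 = 2,004 at Month 11. Adding 29 × 560 = 16,240 gives 18,244 at Month 40, against 18,000 stated (+1.4%). The table is usable as the entry distribution.

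**2. Coverage of the windows.** After Month 24 each window is 28 + 1 + 28 = 57 days wide, and visits are 6 × 30.4375 = 182.6 days apart. Coverage is 57 / 182.6 = 31.2%, so 68.8% of days lie in no window.

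**3. Where V30 lands.** Patients enter at the Table 3 rates, the CSED is at Month 64, and the V30 delay is uniform over 0–30 days:

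V30 day = (64 − entry month) × 30.4375 + delay.

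Each simulated V30 day was compared with the windows. Counts are per 18,000, assuming everyone attends V30 on treatment.

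| Month | Window (days) | Share of V30 samples | Count |
|---|---|---|---|
| 24 | 709–751 | 0.72% | 130 |
| 30 | 885–941 | 5.78% | 1,040 |
| 36 | 1068–1124 | 5.77% | 1,039 |
| 42 | 1250–1306 | 5.77% | 1,038 |
| 48 | 1433–1489 | 5.74% | 1,033 |
| 54 | 1616–1672 | 5.19% | 933 |
| 60 | 1798–1854 | 0.84% | 152 |
| 64 | 1920–1976 | 0.25% | 45 |

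The counts sum to 5,410, and 5,410 / 18,000 = 30.1%. About 70% therefore fall in no window.

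**4. Hand checks.**
- Month 36: a 57-day window takes in 57 / 30.4375 = 1.873 months of entry. At 560 a month that is 1,049 of 18,244, or 5.75%.
- Month 64, no delay: entry within 28 / 30.4375 = 0.92 months. At 32 a month that is 29 patients, 0.16%.
- Month 64, mean delay 15 days: (28 + 15) / 30.4375 × 32 = 45 patients, 0.25%.

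**5. Sensitivity of the 70%.**
- Fixed delay of 0, 14 or 30 days: 69.1–70.2%.
- Uniform accrual over 40 months: about 67–68%.
- Accrual of 30–44 months with the CSED 24–30 months after closing: 67–71%.
- The roughly 600 extra patients from China are not in the simulation. If all of them fell in a window the loss would be 12,600 / 18,600 = 67.7%; if none did, 13,200 / 18,600 = 71.0%.

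**6. A narrower reading of Table 8.** If windows exist only around months when the parameter is scheduled, more is lost under the planned accrual: about 87% for HbA1c, 99% for ApoB and over 99% for hs-CRP.

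**The case against.** The strongest reply is that little depends on these analyses. SAP 3.1.5 calls the endpoints exploratory, and the lipid p-values are descriptive. The on-treatment lipid analysis supplements an ITT analysis that has a CSED value for every lipid. Lp(a) and triglycerides use multiple imputation, and the repeated-measures model has a fallback if it cannot be computed. V30 values still count in the hs-CRP abnormality incidence and, through HbA1c, in new-onset diabetes. All of this stands and limits the reach of the point. None of it returns the V30 values to the hs-CRP summaries or to the on-treatment ApoA-1 and ApoB results.

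One might also say that hs-CRP borrows the LDL-C rules and so inherits the CSED value. The borrowed section, SAP 3.1.5.1, contains only the window rule; the CSED rule is in 3.4.7.4.1.

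A reader might go further than the documents allow:
- **That the protocol's hs-CRP endpoint becomes unobtainable.** The wording in protocol 9.3.3 can describe a span of follow-up, and protocol 11.4.4.2 asks for summaries by time point. Protocol 9.3.2.1 names a terminal time point for lipids; 9.3.3 does not do so clearly for hs-CRP.
- **That the arms are compared with bias.** Whether V30 falls in a window depends on entry date, not on treatment.
- **That hs-CRP at Months 16 and 20 could come only from patients stopping treatment.** Unscheduled samples, and V30 samples from late enrolees in China followed for less than 24 months, can fall there too.

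**Conclusion.** The point holds within these limits. Followed as written, the SAP leaves about 70% of V30 samples (67–71% over the variants tried) out of the by-visit hs-CRP and HbA1c summaries and the on-treatment lipid model. The Month 64 time point would hold about 0.2% of patients, 29 to 45 of 18,000 before any discontinuation.

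The practical loss is in hs-CRP and on-treatment ApoA-1 after Month 12, and on-treatment ApoB after Month 24. There the late profile would be sparse, with a different entry cohort at each point, and could not be read as a time course. LDL-C and HbA1c lose only their last point. No primary or secondary efficacy result and no error rate is touched.

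The figures assume the Table 3 enrolment, a CSED near Month 64, V30 within 30 days of it, and full attendance on treatment. Discontinuation would lower the counts; the share outside the windows would change little.

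**What to change.** - **SAP 3.4.7.1 and 3.4.7.2:** add one descriptive row by arm for the last on-treatment value, meaning the last value up to the last dose + 21 days (normally V30 for completers). Use medians and quartiles for hs-CRP and mean change for HbA1c. SAP 3.4.5.3 already has such a row for the safety laboratory variables.
- **SAP 3.4.7.4.2:** add the same time point as a supplementary on-treatment analysis of ApoA-1 and ApoB, using the covariance model of 3.4.7.4.1. The ITT value at the CSED should remain the end-of-study lipid result, because the on-treatment value is selected on treatment status after randomization.
- **By-month results:** limit hs-CRP and ApoA-1 to Months 4 and 12, and ApoB to Months 4, 12 and 24. State that the near-empty Month 64 contrast will not be interpreted.

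The cost is SAP wording and one derived time point, with no new samples. The new value pools different follow-up durations, as the ITT value at the CSED already does. For patients who stop early it may be an early value, since V70 can fall more than 21 days after the last dose.
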